6.11 Preparation, Reconstitution, and Dispensing

Ixazomib and lenalidomide are anticancer drugs and as with other potentially toxic compounds caution should be exercised when handling ixazomib or lenalidomide capsules.

6.12 Packaging and Labeling

The study drug ixazomib capsules will be provided by Millennium. The study drug will be labeled and handled as open-label material, and packaging labels will fulfill all requirements specified by governing regulations.

The capsules are individually packaged using cold-form foil-foil blisters that are in a child-resistant carton. There are 3 capsules in each wallet/carton.

Lenalidomide will be supplied as commercial product. Standard recommendations from package insert will be followed (See appendix 12.3).

6.13 Storage, Handling, and Accountability

Upon receipt at the investigative site, ixazomib should remain in the blister and carton provided until use or until drug is dispensed. The container should be stored at the investigative site according to storage conditions detailed in the Investigator's Brochure. Ensure that the drug is used before the retest expiry date provided by Millennium. Expiry extensions will be communicated accordingly with updated documentation to support the extended shelf life.

In countries where local regulations permit, ixazomib capsules dispensed to the patient for take-home dosing should remain in the blister packaging and refrigerated as noted above until the point of use. The investigative site is responsible for providing the medication to the patient in the correct daily dose configurations. Comprehensive instructions should be provided to the patient in order to ensure compliance with dosing procedures. Patients who are receiving take-home medication

**Fred Hutchinson Cancer Research Center
Clinical Study Protocol [FHCRC 9266]**

should be given only 1 cycle of medication at a time. Patients should be instructed to store the medication according to storage conditions detailed in the Investigator's Brochure for the duration of each cycle. Patients should be instructed to return their empty blister packs to the investigative site, rather than discarding them. Reconciliation will occur accordingly when the patient returns for their next cycle of take-home medication. Any extreme in temperature should be reported as an excursion and should be dealt with on a case-by-case basis.

Because ixazomib is an investigational agent, it should be handled with due care. Patients should be instructed not to chew, break, or open capsules. In case of contact with broken capsules, raising dust should be avoided during the clean-up operation. The product may be harmful by inhalation, ingestion, or skin absorption. Gloves and protective clothing should be worn during cleanup and return of broken capsules and powder to minimize skin contact.

The area should be ventilated and the site washed with soap and water after material pick-up is complete. The material should be disposed of as hazardous medical waste in compliance with federal, state, and local regulations.

In case of contact with the powder (e.g., from a broken capsule), skin should be washed immediately with soap and copious amounts of water for at least 15 minutes. In case of contact with the eyes, copious amounts of water should be used to flush the eyes for at least 15 minutes. Medical personnel should be notified. Patients are to be instructed on proper storage, accountability, and administration of ixazomib, including that ixazomib is to be taken as intact capsules.

Lenalidomide will be handled per package insert (see Section 12.3)

6.14 Study Compliance

Ixazomib study drug will be administered or dispensed only to eligible patients under the supervision of the investigator or identified sub-investigator(s). The appropriate study personnel will maintain records of study drug receipt and dispensing.

6.15 Termination of Treatment and/or Study Participation

Patients will be informed that they have the right to withdraw from the study at any time for any reason, without prejudice to their medical care. The investigator also has the right to withdraw patients from the study for any of the following reasons:

- Adverse event
- Protocol violation
- Lost to follow-up
- Progressive disease
- Study terminated
- The treatment appears detrimental in the judgment of primary physician

**Fred Hutchinson Cancer Research Center
Clinical Study Protocol [FHCRC 9266]**

- They develop non-hematological, non-metabolic, non-peripheral neuropathy grade IV toxicity
- They are unable to resume therapy more than 30 days after initial stopping of therapy for toxicity or cannot tolerate lowest dose reduction level
- Repeated noncompliance to protocol in view of principal investigator

Patients who are withdrawn from the study will not be replaced.

At the time of withdrawal, all study procedures outlined for the End of Study visit should be completed per study calendar (See Study Flow Chart). The primary reason for patient's withdrawal from the study should be recorded in the source documents and CRF.

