Hypothesis of this phase II study is that ixazomib and lenalidomide as maintenance therapy after autologous PBSC transplant for Multiple Myeloma will be safe and tolerable and prolong the time to disease progression post transplant. The treatment regimen is alternating ixazomib with lenalidomide every two months until disease progression, intolerable toxicity or maximum of 24 months of therapy. The dose of ixazomib is 4.0 mg po on days 1, 8 and 15 per each 28-day cycle given for two consecutive months, followed by then lenalidomide 10 mg po daily for two consecutive months, then ixazomib for two months etc. Dose reduction for toxicity will be incorporated. If >30 days off initially planned next cycle of therapy, then patient will be taken off study. Toxicity will be graded per CTCAE version 4.0. The first four months of therapy will be used as the time period to evaluate end point of toxicity for stopping rules. Toxicity that meets stopping rules will be determined based on the number of patients that are withdrawn from study for significant toxicity (grade IV, non-hematological, non-metabolic, non-peripheral neuropathy) and the number of patients who stop therapy for toxicity and are withdrawn from study as they could not recover adequately and resume therapy by 30 days from the initial stopping of the study drugs. We shall consider the withdrawal rate to be excessive, and hence the therapy to be too toxic, if the true withdrawal rate from the study exceeds 15% in the first four months. An interim analysis at 15 treated patients will be conducted. If > 50% of patients are unable to receive > 50% of planned therapy in first 12 months of treatment, the study will be terminated due to lack of feasibility. Another endpoint is time to disease progression. Patients will be followed for initial response and for progression of disease, response criteria will be determined by International Myeloma working group criteria. In patients with chemo-refractory disease at the time of ASCT, the therapy will be felt to be promising if median time to progression is >9 months. If chemo-sensitive disease at time of ASCT, the therapy will be felt to be promising if median time to progression is >41 months based on CALGB 10014 lenalidomide maintenance study post ASCT. Cytogenetic information will be collected and initial response rates and outcome will be descriptively reported. Patients will be followed for overall survival. The incidence of secondary cancers will also be collected. If this study regimen is deemed to be potentially efficacious and is not regarded as too toxic per stopping rules outlined above and observed EFS rate are consistent with rates that match or exceed historical benchmarks, then a phase III trial to show efficacy rate of this regimen over single agent therapy will be designed.

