7.1.7 Safety Analysis

The first endpoint is to evaluate the toxicity of the proposed therapy. The first four months of therapy will be used as the time period in which toxicity will be evaluated and stopping rules for unacceptable toxicity will be implemented. Rules for stopping therapy will be based on rate of withdrawal due to significant toxicity (grade IV, non-hematological, non-metabolic and non-peripheral neuropathy). A true withdrawal rate within first 4 months of 15% will be considered excessive. Withdrawal rate will be assessed after every ten patients are treated. Enrollment will not be held though until the 10th patient enrolled becomes evaluable. Sufficient evidence will be taken for a lower limit to the corresponding one sided 80% confidence interval that exceeds 15%. Operationally observed rates that say regimen is too toxic would be 2/5, 3/10, 4/15, 5/20, 6/25 and 7/30. If the true probability of withdrawal from the study is 5%, the probability of deeming this regimen as too toxic after 15 or 30 patients have been treated is approximately .03 and .03, respectively. If the true probability of withdrawal is 10%, these probabilities are approximately .13 and .15, respectively. On the other hand, if the true probability of withdrawal is .30, then the probability of judging this regimen as too toxic after 15 or 30 patients is approximately .78 and .91, respectively.

With the semi-continuous monitoring of the withdrawal rate, the estimate of this rate, should the study run to completion, will be biased slightly downward. Without consideration of this bias, 30 patients will allow us 80% confidence that the estimated withdrawal rate will be within approximately .094 of the true rate under the assumption that the true rate is 20%. The incidence of second cancers will also be collected.

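### The toxicity stopping rule counts fewer toxicity withdrawals than Section 6.15 allows, although its 15% limit is stated for withdrawal from the study

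*Combined protocol and SAP*

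**What the plan says.** Three places bear on what counts as an event.

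- **Section 7.1.7** bases the rule on the "rate of withdrawal due to significant toxicity (grade IV, non-hematological, non-metabolic and non-peripheral neuropathy" category alone. It calls a true four-month withdrawal rate of 15% excessive and gives boundaries of 2/5, 3/10, 4/15, 5/20, 6/25 and 7/30.
- **Protocol Summary, Overview of Study Design,** counts two groups: patients "withdrawn from study for significant toxicity (grade IV, non-hematological, non-metabolic, non-peripheral neuropathy", and patients who "stop therapy for toxicity and are withdrawn from study as they could not recover adequately and resume therapy by 30 days". It states the 15% limit for the true rate of withdrawal from the study in the first four months, without repeating either restriction.
- **Section 6.15** lists the reasons for which the investigator may withdraw a patient. Two match the Summary's components. Others are a plain adverse event, "The treatment appears detrimental in the judgment of primary physician", and, as an alternative to the 30-day reason, "or cannot tolerate lowest dose reduction level". Withdrawn patients are not replaced. The section also requires that "The primary reason for patient's withdrawal from the study should be recorded in the source documents and CRF".

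Section 7.1.8 makes planning of a phase III trial depend in part on the regimen not being judged too toxic under these rules.

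**The concern.** The limit is expressed as a withdrawal rate, but the count is a subset of withdrawals. A patient withdrawn for a grade 3 reaction before 30 days have passed has left the study for toxicity and is an event under neither definition. The same holds for a patient withdrawn because the lowest dose level cannot be tolerated, unless that patient also meets a counted criterion. Each stays in the denominator as a tolerated case.

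Toxicity is the only primary endpoint, and this rate is the only primary quantity with a threshold, boundaries and a precision statement. If some toxicity withdrawals are missed, the rule is less likely to stop a regimen whose overall toxicity-withdrawal rate is excessive. The reported rate would also fall below what a reader would take it to measure. Section 7.1.7 already accepts a slight downward bias from repeated monitoring; this effect would be additional and is not mentioned.

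**Working it through.** **1. Withdrawal reasons against event definitions**

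| Reason in Section 6.15 | Section 7.1.7 | Protocol Summary |
|---|---|---|
| Grade IV toxicity outside the three excluded classes | counted | counted |
| Toxicity stop, unable to resume past 30 days | not named | counted |
| Cannot tolerate lowest dose level | not named | not named; counted only if a row above also applies |
| Adverse event | only if qualifying grade IV | only if qualifying grade IV or the 30-day criterion is met |
| Treatment appears detrimental | not named | not named; may or may not be toxicity |

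Adding the 30-day component to Section 7.1.7 would align the two definitions. The third row, and adverse-event withdrawals below grade IV before 30 days, would still be outside both.

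**2. The plan's own figures**

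Inputs: the six boundaries in Section 7.1.7. Method: exact sequential binomial. At each look n, the probability that the count first reaches the boundary is added to the total, and only uncrossed paths are carried forward.

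First look at a rate of .30: P(at least 2 of 5) = 1 − .7⁵ − 5(.3)(.7⁴) = 1 − .168 − .360 = .472.

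Continuing with looks every five patients:

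| True rate | By 15: computed (stated) | By 30: computed (stated) |
|---|---|---|
| 5% | .030 (.03) | .031 (.03) |
| 10% | .129 (.13) | .146 (.15) |
| 30% | .775 (.78) | .912 (.91) |

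All six reproduce. Section 7.1.7 says the rate is assessed after every ten patients. On that schedule the 30-patient values are .013, .096 and .892, so the stated figures belong to the five-patient schedule. These figures take the event rate as given. They show that the rule is computed correctly for whatever is counted, and say nothing about what should be counted.

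**3. Effect of incomplete capture (illustration)**

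Let P be the true four-month toxicity-withdrawal rate and c the share that the event definition captures. The monitored rate is c × P. The documents do not give c; the values below are assumptions. For P = .30 the monitored rates are .9 × .30 = .27, .75 × .30 = .225 and .5 × .30 = .15.

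| Share captured | P = .30, looks every 5 | P = .30, looks every 10 | P = .20, looks every 5 |
|---|---|---|---|
| 100% | .91 | .89 | .59 |
| 90% | .85 | .82 | .50 |
| 75% | .70 | .65 | .35 |
| 50% | .35 | .29 | .15 |

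Entries are probabilities of stopping by 30 patients.

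**4. How few patients matter**

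At 30 patients, 7 events give a one-sided 80% exact lower limit of .161, above 15%; 6 events give .133, below it. If seven of 30 patients left for toxicity and one did so by an uncounted route, the count would be 6/30 and the boundary would not be met at that look.

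**The case against.** Several counter-arguments have force.

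- **Overlap.** A reader might infer that adverse-event withdrawals go uncounted as a class. They do not. A qualifying grade IV event is counted in both definitions, and the Summary's 30-day component has no grade or class restriction. Grade 4 neuropathy is a tempting example of a total omission, but Table 6-3 directs discontinuation of ixazomib, which is an action on one drug and not a study withdrawal. If the patient is later withdrawn for not resuming within 30 days, the Summary counts the case, although Section 7.1.7 as worded does not.
- **Usual route.** Tables 6-3 and 6.5 direct a hold for grade 3 non-hematological toxicity, so withdrawal before 30 days is permitted by Section 6.15 but is not the tabulated path.
- **Rarity.** Table 6-1 has three steps from the starting ixazomib dose to discontinuation, and the four-month window holds two ixazomib cycles of three doses each. Table 6.4 has three lenalidomide reductions, also against two cycles. Floor-dose intolerance may be rare in the window.
- **Detriment** need not mean toxicity.
- **Deliberate restriction.** The plan limits its first component to significant toxicity, and the estimate is not biased for an event so defined.
- **Feasibility rule.** Under Section 7.1.8, a patient withdrawn within four months has received at most 4/12, one-third, of the first year's therapy and so counts there whatever the reason.

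These points limit the likely size. They do not close the gap. If the restriction is deliberate, the 15% limit should be stated for the restricted event, and it is not. The feasibility rule needs more than half of patients, at least 8 of 15, against 4 of 15 for toxicity, so it is no substitute.

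**Conclusion.** The concern holds as a gap in definition. Neither event definition covers all the toxicity withdrawals that Section 6.15 permits: intolerance of the lowest dose level, and withdrawal for an adverse event below grade IV before the 30-day limit, are outside both. Relative to all toxicity withdrawals, the omission can only lower the monitored rate. It has no effect if no such withdrawals occur in the first four months.

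The size is unknown. The fall from .91 to .85, .70 or .35 rests on an assumed true rate of 30%, assumed capture of 90%, 75% or 50%, and looks every five patients. A reader might infer that the rule is known to be badly underpowered; the documents do not support that, because they give no rate for the uncounted routes. Nor do they support extending the event to discontinuation of one drug in patients who remain on study, since the limit is stated for withdrawal from the study.

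**What to change.** Reconcile the Protocol Summary, Section 6.15 and Section 7.1.7 into one event definition, worded identically in the Summary and Section 7.1.7. Count every patient withdrawn from the study in the first four months whose primary reason on the CRF is toxicity. That covers the grade IV, 30-day and lowest-dose reasons, and the adverse-event and detriment reasons where toxicity is the cause. Report the grade IV subset separately. Do not count discontinuation of a single drug in a patient who stays on study.

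The change is to wording and tabulation: the primary reason is already collected, and no treatment or withdrawal rule changes. The cost is that boundaries may be reached sooner. If, purely as an assumption, the wider event raised the rate from 10% to 20%, the probability of stopping by 30 patients would rise from .15 to .59 with looks every five. The sponsor should therefore confirm that the 15% limit is meant for this event. If the sponsor intends the narrower event, the 15% limit and the stated probabilities should be labelled as applying to it.

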7. STATISTICAL AND QUANTITATIVE ANALYSES

7.1 Statistical Methods

Research Description To see if alternating ixazomib with oral lenalidomide is well tolerated with acceptable toxicity profile post ASCT and if it provides equivalent or superior outcomes in terms of time to disease progression over lenalidomide alone.

7.1.1 Determination of Sample Size

Thirty Multiple Myeloma patients post ASCT are to be enrolled over 2-3 years. Expect to enroll 1-1.5 patients per month.

7.1.2 Randomization and Stratification

There is no randomization or stratification of patients on this study.

7.1.3 Populations for Analysis

Multiple Myeloma patients post ASCT.

7.1.4 Procedures for Handling Missing, Unused, and Spurious Data

Data collection will be evaluated quarterly for record completeness. Any missing data will be abstracted from primary source files. Study-specific case report forms (CRFs) will specify required data to be collected to ensure that patient safety and study objectives are accurately and completely captured. Primary source documents will be stored with all CRFs to provide validity for the abstracted data.

7.1.5 Demographic and Baseline Characteristics

Patients will be characterized as to whether they are chemo-sensitive or chemo-refractory disease at time of autologous transplant. All patients with PR or better response to last standard chemotherapy will be considered to have chemosensitive disease. Cytogenetic information will be collected.

7.1.6 Efficacy Analysis

An endpoint of the study is time to disease progression. Patients will be followed for initial response and for progression of disease. Response criteria will be determined by International Myeloma Working Group Criteria. In patients with chemo-refractory disease at the time of ASCT, the therapy will be felt to be promising if median time to progression is >9 months. If chemo-sensitive disease at time of ASCT the therapy will be felt to be promising if median time to progression is > 41 months based on CALGB 10014 lenalidomide maintenance study post ASCT. Initial response rates and outcome will be descriptively reported. Patients will be followed for overall survival.

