Differences in results may be due to differences in design of study, dose of thalidomide given, number of patients treated, use with steroids and type of steroid, comparison group, prior use of thalidomide in induction, duration of therapy and follow-up interval. In general, all have statically shown better event free survival (efs)/progressive free survival (pfs) in thalidomide arms of study, four reported increase in response rates, three studies had increase in OS. Thalidomide seems though to do best in standard risk disease. Peripheral neuropathy was an issue though in the studies and did result in discontinuation of drug. Little data about CR after ASCT and if those patients benefited by addition of thalidomide though was presented. IFM study 99-02 reported most benefit of thalidomide was in patients less than VGPR after ASCT^[23] but MRC My IX study did not see difference in benefit based on response to ASCT^[27]. Recently, Rawstron AC et al^[31] showed in clinical trial setting MRD can be used to track efficacy of maintenance therapy as 8 out of 29 patients with MRD positive after ASCT randomly assigned to thalidomide maintenance became MRD negative vs. only one out of 29 not receive maintenance therapy.

Combination therapy with thalidomide has also been studied as consolidation after ASCT. Cavo et al^[32] reported that after tandem ASCT the PFS for VTD was superior to TD. The beneficial effect was most evident in patient not achieving at least near CR after ASCT in the initial report.

Lenalidomide

Lenalidomide was the next drug studied to be given after ASCT. The largest randomized studies has been CALGB^[33] and the IFM study^[34] that used maintenance or consolidation/maintenance approaches. See tables 1.7 and 1.8 for summary of design of studies, comparisons of studies and outcomes.

Table 1.7 CALGB vs. IFM Lenalidomide Studies

Study	# pts	Therapy	EFS	OS	Duration Therapy
CALGB 10014 [33]	462	Induction pre TX: Thal and Len 74%, and no progression during induction allowed All got single ASCT Cons: No Maint: 10 mg Len vs. Placebo	3 yr EFS 43 vs. 27 mos (p<.001)	85 vs. 77%, p=.028 Med fu 34 mos Superior S even with crossover	Crossover Range Len exposure 30-72 mos All continue on therapy

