7.1.8 Interim Analysis

An interim analysis at 15 treated patients will be conducted to assess feasibility for maintenance therapy. If > 50% of patients are unable to receive > 50% of planned therapy in first 12 months of treatment, the study will be terminated due to lack of feasibility.

If this study regimen is deemed to be potentially efficacious and is not regarded as too toxic per stopping rules outlined above and observed EFS rate are consistent with rates that match or exceed historical benchmarks, then a phase III trial to show efficacy rate of this regimen over single agent therapy will be designed.

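### A single-arm trial of 30 with a bare 41-month median threshold cannot show equivalence or superiority to lenalidomide alone, and the plan does not say how an unreached median is scored

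*Combined protocol and SAP*

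**What the plan says.** Section 7.1 states the efficacy question as whether the alternating regimen gives "equivalent or superior outcomes in terms of time to disease progression over lenalidomide alone". Section 7.1.2 says: "There is no randomization or stratification of patients on this study". Section 7.1.1 sets the number of patients ("Thirty Multiple Myeloma patients post ASCT are to be enrolled over 2-3 years") and gives no efficacy basis for it.

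Section 7.1.6 holds two thresholds. For chemo-sensitive disease, "the therapy will be felt to be promising if median time to progression is > 41 months based on CALGB 10014". For chemo-refractory disease, "the therapy will be felt to be promising if median time to progression is >9 months". Neither has an interval, test, error rate or margin, or a rule for a median that is not reached. The same section says that response rates and outcome will be reported descriptively.

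Section 7.1.8 makes a phase III trial conditional on potential efficacy, on acceptable toxicity, and on whether "observed EFS rate are consistent with rates that match or exceed historical benchmarks". Table 1.7 (section 1.10.1) gives the CALGB 10014 result as "3 yr EFS 43 vs. 27 mos (p<.001"), lenalidomide against placebo.

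**The concern.** The question in 7.1 is comparative, and nothing in the design can answer it. There is no concurrent lenalidomide arm, no margin that would define equivalence, and no interval to hold against one. What remains is an observed median set against a fixed number. The threshold is long relative to follow-up, so in many trials the median may not exist when the data are analysed, and the plan does not say whether that counts as a pass.

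Two things are at stake. A final report could state equivalence or superiority on the strength of a pass that a moderately worse regimen would also achieve fairly often. And in the unreached case, the label would be settled after the data are seen.

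**Working it through.** **1. The plan's own precision figure.** Section 7.1.7 says that 30 patients put the estimated withdrawal rate within about .094 of a true 20%, with 80% confidence. Check: 1.2816 × √(0.20 × 0.80 / 30) = 0.0936. It reproduces. No corresponding figure exists for the efficacy rule.

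**2. Inputs.** Accrual A = 24 to 36 months and F = 24 months after the last start (section 4.3). Chemo-sensitive patients n = 20 to 30 (assumed, because section 7.1.5 defines the group but gives no number). Exponential time to progression and uniform accrual (assumed).

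**3. Expected progressions at a true median of 41 months.** λ = ln 2 / 41 = 0.01691 per month, and P(progression observed) = 1 − e^(−λF) × (1 − e^(−λA)) / (λA).
- A = 24: 1 − 0.6665 × 0.3335 / 0.4057 = 0.452, so 9.0 (n = 20) to 13.6 (n = 30) events.
- A = 36: 1 − 0.6665 × 0.4559 / 0.6086 = 0.501, so 10.0 to 15.0 events.

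About 3 to 8 patients are still at risk at 41 months.

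**4. Pass probability of the rule.** Simulation of 20,000 trials per setting, with the median taken as the first time at which the Kaplan-Meier curve is at or below 0.5. An unreached median counts as above 41.

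| True median (months) | P(pass) |
|---|---|
| 41 | about 50% |
| 33 (hazard ratio 41/33 = 1.24) | 21-28% |
| 27 | 6-11% |

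At a true 41 months the median is not reached in about 20-43% of trials. If follow-up runs to the five years given as the study duration in the protocol summary, this falls to about 15-26%. If a pass requires a median that is actually reached, the 50% becomes about 8-30%. The 50% barely moves under Weibull shapes 0.8 and 1.3 (49-51%) or with 10% annual loss (51-52%).

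**5. Precision around an observed 41 months.** Approximate exponential limits, 41 × exp(±z/√d), for d = 10 and d = 15 events:
- Two-sided 95%: 22 to 76, and 25 to 68 months.
- One-sided 90% lower bound: 41 × exp(−1.2816/√d) = 27.3 and 29.4.
- One-sided 80% lower bound: 41 × exp(−0.8416/√d) = 31.4 and 33.0.

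**6. A landmark that can be estimated.** Every patient has potential follow-up to 24 months. Under an exponential model the 24-month progression-free probability is 0.5^(24/41) = 0.67 at a median of 41 months, 0.5^(24/33) = 0.60 at 33 and 0.5^(24/27) = 0.54 at 27. Without losses, the 95% half-width at 0.67 is 1.96 × √(0.67 × 0.33 / n), which is 0.21 for n = 20 and 0.17 for n = 30. The landmark is always available, but it does not separate 41 from 33 months either.

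**The case against.** The case for the plan is substantial, and most of it stands.

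- *A reader might infer that a 50% pass rate at 41 months is a false-positive rate.* It is not. A true 41 months is the benchmark, and any threshold set at the benchmark passes about half the time there. The figure also depends on counting an unreached median as a pass.
- *A reader might infer that the rule cannot screen out the no-maintenance result.* The figures say otherwise, since a true 27 months is rejected about 89-94% of the time. A two-sided 95% interval around an observed 41 does include 27, but no section sets that level for efficacy. At the one-sided 80% level that section 7.1.7 uses for toxicity, the lower bound is 31 to 33 months.
- *A reader might infer that a promising result alone leads to phase III.* Section 7.1.8 also requires acceptable toxicity and a consistent EFS rate. Toxicity is the primary endpoint, and sections 1.1.1 and 7.1.8 leave the comparison with single-agent therapy to a later trial. No section equates *promising* with *equivalent or superior*.
- *A reader might infer that 41 is a misquotation of 43.* The first is labelled TTP and the second EFS. Endpoint, time origin or data cut could differ. The mismatch is unexplained but not a proven error.
- *Requiring a lower bound above 41 months would not work here.* A one-sample test at one-sided 10% with 80% power for a hazard ratio of 0.67 needs (1.2816 + 0.8416)² / (ln 0.667)² ≈ 28 events. The design yields about 7 to 11 under that alternative.

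None of this rescues the comparative wording in 7.1 or fills the gap on the unreached median.

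**Conclusion.** The concern holds in a limited form. The equivalence-or-superiority aim goes beyond what a single-arm trial of 30 without a margin can show, because a regimen with a true median of 33 months still passes about 21-28% of the time. The threshold is usable as a screen against 27 months. It is not evidence of parity with lenalidomide. The plan also leaves open an outcome that is expected in about 20-43% of trials at the benchmark. If 43 months is the true lenalidomide median, a regimen no better than lenalidomide passes 54-57% of the time, so the benchmark mismatch matters less than the imprecision.

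These sizes rest on an assumed 20 to 30 chemo-sensitive patients, exponential progression times and the follow-up in section 4.3. They describe the chemo-sensitive efficacy criterion alone, not the joint phase III decision.

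**What to change.** - **Section 7.1:** replace the comparative clause with 'whether time to progression is promising against a historical benchmark'.
- **Section 7.1.6:** keep *promising* as a screening label. State how an unreached median is treated. Report the Kaplan-Meier median and the 24-month progression-free probability with confidence intervals (95%, or the one-sided 80% level already used in 7.1.7). State the rule's pass probabilities at true medians of 27, 33-35 and 41 months, as 7.1.7 does for withdrawal rates.
- **Sections 7.1.6 and 7.1.8:** use one endpoint, TTP or EFS, throughout. Give a source for the 41-month TTP threshold or reconcile it with the 43-month EFS in Table 1.7.

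The cost is wording and routine output, with no additional patients or visits. The downside is that the efficacy statement becomes weaker. The intervals will be wide and will not by themselves supply a pass criterion, so the decision on a phase III trial remains a judgement that also takes in toxicity and the EFS condition in 7.1.8.
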